9.6.1. Adverse Events

Adverse events will be coded using the Medical Dictionary for Regulatory Activities (MedDRA v 26.1) or more recent version.

A treatment related adverse event will be considered a TEAE if it starts on/after the time of study (iovera^o or RFA) treatment. If an AE has a partial onset date and time, the imputed start dates will be used to determine treatment-emergence (**Section 9.1.1.2**).

All summaries of AEs will include AEs that occur after the start of iovera^o treatment. Events that start prior to iovera^o treatment will be identified in listings only.

AEs will be summarized using subject incidence table. An overview of AEs will be presented. This table will include n (%) of subjects with:

- Any TEAE
 - Maximum severity: Mild
 - Maximum severity: Moderate
 - Maximum severity: Severe
- At least one related TEAE
- At least one serious TEAE
- Subjects discontinued due to a TEAE
- Serious treatment-emergent adverse events (TESAEs)
- Died on study.

Additionally, n (%) are calculated based on the number of unique subjects within each MedDRA category (e.g., preferred term) by treatment group. A subject reporting multiple events of the same category will be counted only once for that category. For summary purposes, AE relationship to the iovera^o or RFA will be grouped into “Unrelated” for “unrelated” or “unlikely related” and “Related” for “possible”, “probably”, or “definite”. For subjects with more than one event coded to the same PT, the subjects will be counted for the categories with the strongest relationship and the greatest severity. The following subject incidence tables will be presented:

- TEAEs by PT (Preferred Term) sorted by the decreasing order of subject incidence in the combined group
- TEAEs by SOC (System Organ Class) and PT sorted alphabetically
- TEAEs treatment-related by SOC and PT
- TEAEs by severity and by SOC and PT

- TESAEs by SOC and PT.

A data listing will be provided for all AEs. Included in the listing are the reported term, PT, SOC, TEAE and TESAE flag, study day when AE starts, duration, relationship to treatment(s), severity, action taken, outcome, and seriousness category.

Separate data listings will be provided for subjects who experience SAEs and die on study.

9.6.2. Adverse Device Effects

Any untoward medical occurrence, unintended disease or injury, or untoward clinical signs (including abnormal laboratory findings) associated with the use of a device in subjects, whether or not considered related to the device. This also includes adverse device effects related to the use of a device resulting from failure, insufficient or inadequate instructions for use, improper or inadequate design, deployment, implantation, installation, or operation, or any malfunction of the device, as well as any event resulting from user error (or use error) or from intentional misuse of the device.

Serious adverse device effects are categorized by any of the following which results in any of the consequences characteristic of a serious adverse event:

- Results in death
- Is immediately life-threatening (i.e., an event in which the subject was at risk of death at the time of the event. It does not refer to an event, which hypothetically may have caused death, if it were more severe)
- Requires in-patient hospitalization or prolongation of existing hospitalization
- Results in persistent or significant disability or incapacity (i.e., a substantial disruption of a person's ability to conduct normal life functions)
- Is a congenital anomaly or birth defect
- Is an important medical event where medical and scientific judgment should be exercised in deciding whether SAE reporting is appropriate, such as events that may not be immediately life-threatening or result in death or hospitalization but may jeopardize the participant or may require medical or surgical intervention to prevent one of the other outcomes listed in above definition. Examples of such events include intensive treatment in an emergency room or at home for allergic bronchospasm, blood dyscrasias or convulsions that do not result in hospitalization, or development of drug dependency or drug abuse.

The incidences of death, serious injury, or malfunction resulting from the device will be summarized for each treatment group.

9.6.3. Study Stopping Rules

The study may be terminated if the Investigator, or officials from regulatory authorities, identify conditions during the study that indicate so.

The Investigator will review all serious adverse device effects and serious adverse events (SAEs) reported from the clinical study on an ongoing basis and in real time (i.e., as the events are reported). The Investigator will be responsible for temporarily halting the study if the type, frequency, or seriousness/severity of such events suggests a potential threat to the safety of the study participants. If such action is taken, a thorough review of all available data will be conducted. Based on the results of this review and discussions with the investigator and/or regulatory authorities as warranted, the study may be restarted or permanently terminated.

The following adverse event study stopping rules will be applied:

[REDACTED]

In addition, any death will be thoroughly reviewed, and appropriate action taken.

9.6.4. Determination Study Success

[REDACTED]

9.7. Efficacy Analysis

For efficacy analyses, descriptive statistics that are appropriate for the efficacy variable will also be shown by treatment.

9.7.1. Efficacy Endpoints

9.7.1.1. Primary Endpoint

NRS “average pain over past 24 hours” intensity scores from first pain assessment post-treatment (24 hr) to Day 360

9.7.1.2. Secondary Endpoints

The following endpoints are secondary efficacy endpoints:

- NRS "average pain over past 24 hours" intensity scores from first pain assessment post-treatment (Day 1) to Day 30, Day 180, and Day 360
- Changes in NRS pain intensity scores ("average pain over 24 hours") from pre-treatment to Day 360
- Oswestry Disability Index scores (ODI) from Day 30 to Day 360
- Change in Oswestry Disability Index (ODI) scores from pre-treatment to Day 360
- Patient's Global Impression of Change (PGIC) scores from Day 30 to Day 360
- Patient satisfaction with pain management from Day 30 to Day 360
- Percentage of subjects who are in "no disability" determined by ODI scores at Day 360
- Concomitant medication use

9.7.2. Methods of Analysis

For Primary and Secondary Efficacy Analyses, descriptive statistics (number of subjects, mean, SD, median, minimum, and maximum) will be provided for continuous data. Tabulations (number and percentage of subjects) by category will be provided for categorical data. All efficacy analyses will be performed on the efficacy analysis set.

9.7.2.1. Primary Efficacy Analysis

9.7.2.1.1. NRS "average pain over past 24 hours" Intensity Score scores from first pain assessment post-treatment (Day 1) to Day 360

The primary analysis of the primary efficacy endpoint will compare the iovera^o and RFA group. The superiority of iovera^o to RFA will be evaluated based on the following null hypothesis and alternative hypothesis:

H₀: iovera^o is not superior to RFA with respect to mean of NRS pain intensity scores at Day 360

H_a: iovera^o is superior to RFA with respect to mean of NRS pain intensity scores at Day 360

A two-sided hypothesis test will be performed at $\alpha=0.05$ level of significance comparing EXPAREL and bupivacaine HCl as follows:

- If the two-sided p-value for the least squares mean treatment difference in NRS at Day 360 (iovera^o- RFA) is >0.05 , then the superiority of iovera^o to RFA is not achieved.
- If the p-value for the least squares mean treatment difference in NRS at Day 360 (iovera^o- RFA) is ≤ 0.05 , then the superiority of iovera^o to RFA is achieved.

Least Squares Means (LSM) of “average pain over 24 hours” at Day 360 will be calculated for each subject. LSM for “average pain over 24 hours” at Day 360 will be summarized by treatment group, and overall.

To test for significant differences between iovera^o and RFA group, a Linear Regression Model with adjustment of baseline NRS, sex, and tobacco status was used. The LS means for each treatment group, two-sided 95% CI for the LS mean difference, and p-value will be presented.

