The total duration of study follow-up will be 12 months after the iovera^{\circ} or RFA procedure. Adverse device effects, serious adverse device effects, adverse events (AEs), and serious adverse events (SAEs) will be recorded from the time the study ICF is signed through Day 360 (± 7 days). Any concomitant medications used to treat AEs through Day 360 (± 7 days) will also be recorded.

Statistical Methods:

As the aim of this pilot study is not to assess effectiveness or efficacy, formal hypothesis testing will not be determined, and sample size will not be calculated based on desired statistical power to detect a treatment effect.

A total of 30 subjects are planned for this pilot study, with 15 randomized to each of the 2 study groups.

Descriptive statistics (number of subjects, mean, SD, median, minimum, and maximum) will be provided for continuous data. Tabulations (number and percentage of subjects) by category will be provided for categorical data. Safety data will be summarized descriptively by treatment groups and overall, and no statistical testing for comparison of treatment groups will be performed for safety variables.

Day 180 Visit

±5d

X X

> → X

	Screen Visit	ioveraº /RFA	24h to 144h	Day 7 Call	Day 15 Call	Day 30	Day 60 Call	Day 90 Call	Day 120	Day 150
		treatment	post-block	Can	Can	Visit	Call	Can	Can	Call
			Call							
Time	≤30 days pre-	Day 1	±4h	±2d	±3d	±5d	±5d	±5d	±5d	±5d
Window	block	-								
Obtain signed ICF	Х									
Assess/confirm eligibility	Х	Х								
Record demographics and baseline characteristics	Х									
Record/update medical and surgical history	Х	Х								
Record/update prior/concurrent medications and therapies	Х	Х								
Measure vital signs ¹	Х	Х								
Perform physical examination per standard of care	Х									
Perform neurological examination per standard of care	Х									
Record NRS pain intensity scores (pain "right now") ²	•									
Record history of workers' compensation, personal injury,	v									
SSDI, or other litigation related to the spine	Λ									
Record NRS pain intensity scores (worst / average pain over	х		-							
24h)							37	37	37	
Administer the Oswestry Disability Index	X					X	Х	X	X	X
Administer the PGIC						X	X	X	X	X
Administer iovera ^o /RFA treatment, record start & stop times		Х								
of procedure		v								
Capture radiographic images		X								
Record concomitant medications (including opioids and										
Depend subject satisfaction with pain management						v	v	v	v	v

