6. STUDY OVERVIEW

[figure not shown]
This is a single-center, randomized, pilot study in adult subjects with facet-mediated CLBP. Thirty (30) subjects are planned for initial enrollment and will be randomized 1:1 to receive iovera^o medial branch cryoneurolysis or radiofrequency ablation.

This study is designed to determine if a full efficacy RCT can be successfully conducted using the procedures and protocols described in the current pilot study protocol, or if protocol modifications are necessary before moving forward with a full efficacy RCT. Furthermore, the study will assess the feasibility of the outcome measurements employed, construct a foundation for sample size calculation, and the acceptability/practicality of conducting the full efficacy RCT.

Randomization to treatment groups according to the randomization assignment will be performed on the day of treatment. The treatment groups are:

- **Group 1:** subjects will receive iovera^o cryoneurolysis of the medial branch nerves
- **Group 2:** subjects will receive RFA of the medial branch nerves

Figure 1 Study Schema

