10. SAMPLE SIZE CALCULATIONS

As the aim of this pilot study is not to assess effectiveness or efficacy, formal hypothesis testing will not be determined, and sample size will not be calculated based on desired statistical power to detect a treatment effect. A total of 30 subjects are planned for this pilot study, with 15 randomized to each of the 2 study groups.

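### SAP 9.7.2.1.1 orders a superiority test with a pass/fail verdict that the protocol and SAP Section 10 rule out, and its test sentence names products that are not the trial's arms

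*SAP*

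**What the plan says.** SAP Section 9.7.2.1.1 covers NRS average pain over 24 hours, with the comparison at Day 360. It opens: "The superiority of iovera^o to RFA will be evaluated based on the following null hypothesis and alternative hypothesis". A null and an alternative hypothesis follow, then a two-sided test at 0.05, which the SAP describes as "comparing EXPAREL and bupivacaine HCl as follows". Two decision rules come next. A p-value above 0.05 means superiority is not achieved; for a p-value of 0.05 or less, "then the superiority of iovera^o to RFA is achieved". The linear regression, adjusted for baseline NRS, sex and tobacco status, is introduced with "To test for significant differences between iovera^o and RFA group". LS means, a two-sided 95% CI for their difference and a p-value are to be reported.

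SAP Section 10 says: "As the aim of this pilot study is not to assess effectiveness or efficacy, formal hypothesis testing will not be determined". The protocol has the same sentence under Statistical Methods: "formal hypothesis testing will not be determined, and sample size will not be calculated based on desired statistical power". Both plan 30 subjects, 15 per group.

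The arms are set out in SAP Section 6: Group 1 receives iovera cryoneurolysis, and for Group 2, "subjects will receive RFA of the medial branch nerves". The same section gives one purpose of the pilot as to "construct a foundation for sample size calculation".

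**The concern.** One part of the SAP requires a formal test with a binary verdict. Another part of the SAP, and the protocol above it, say there will be none. If this is left open until the data are in, the choice between claiming superiority and reporting that nothing was formally tested can be made with the results in view.

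The verdict would also be issued on a sample that was not sized for it. At 15 per arm, 'superiority not achieved' could easily be read as evidence against iovera when it mostly reflects the small sample. The pilot's stated use is to inform the sample size of a full trial. An estimate with its interval serves that use; a pass/fail label adds nothing to it.

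Two further faults sit in the same section. The test sentence names products that are not the study arms. The success rule gives no sign for the difference, so a significant result favouring RFA would meet it literally. The alternative hypothesis is directional and the CI is reported, so the second of these is a matter of wording.

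**Working it through.** **Text comparison**

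| Question | SAP 9.7.2.1.1 | SAP 10 and Protocol, Statistical Methods |
|---|---|---|
| Is a hypothesis tested? | Yes: null and alternative stated, two-sided 0.05 | No formal testing |
| Is efficacy an aim? | Superiority is to be judged | The aim is not efficacy or effectiveness |
| What is the output? | Achieved / not achieved | No such verdict foreseen |

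Three other places agree with the right-hand column. The primary objective in both documents is safety and feasibility. SAP Section 9.7.2 describes the primary and secondary efficacy analyses by descriptive statistics. No power, SD or target difference is given anywhere.

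EXPAREL appears nowhere else in the documents. Bupivacaine otherwise appears only as a local anaesthetic within the RFA procedure. The hypotheses, both decision rules and the model sentence name iovera and RFA, so the intended comparison is clear. Only the sentence setting alpha is wrong.

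Sections 9.7.2.2.1 to 9.7.2.2.5 apply the same analysis to five secondary endpoints (9.7.2.2.2 without covariates), so the conflict reaches most of the efficacy results.

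**What the verdict would be worth**

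The plan's own figure is 15 × 2 = 30. It has no power calculation behind it, so nothing more can be reproduced. The rest is illustration.

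Inputs from the documents: 15 per arm; two-sided 0.05; regression with treatment, baseline NRS, sex and tobacco status.

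Assumptions: residual SD 1.5 to 3.0 NRS points; true benefit of 1 or 2 points; no dropout; tobacco status in two levels; no chance imbalance in the covariates.

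- Residual df = 30 − 5 = 25 (intercept, treatment and three covariates); critical t = 2.060.
- SE = SD × √(2/15). For SD 2.0: 2.0 × 0.3651 = 0.730.
- 95% CI half-width = 2.060 × SE. For SD 2.0: 2.060 × 0.730 = 1.50.
- P(not achieved) = probability that |t| is below 2.060, with t noncentral on 25 df and noncentrality equal to true difference / SE. For SD 2.0 and 1 point: noncentrality 1/0.730 = 1.37, giving 0.739.
- The difference detectable with 80% power solves the same expression for 0.20, which gives 1.064 × SD.

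| SD | SE | CI half-width | 80%-power difference | P(not achieved), 1 point | P(not achieved), 2 points |
|---|---|---|---|---|---|
| 1.5 | 0.548 | 1.13 | 1.60 | 0.581 | 0.061 |
| 2.0 | 0.730 | 1.50 | 2.13 | 0.739 | 0.251 |
| 2.5 | 0.913 | 1.88 | 2.66 | 0.816 | 0.442 |
| 3.0 | 1.095 | 2.26 | 3.19 | 0.858 | 0.581 |

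Allowing for chance covariate imbalance widens the half-width slightly, to about 1.2 to 2.4 points, and moves P(not achieved) at 1 point to about 0.62 to 0.87.

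**The case against.** The best defence is that Section 10 only explains why the sample was not powered. It sits under a sample-size heading. The explicit bar on between-group testing, in both documents, is limited to safety variables, a limit that would be needless if all testing were barred. The SAP introduction refers to study hypotheses, and two secondary objectives compare iovera with RFA on clinical outcomes and on treatment success. On this reading the test could stay if labelled exploratory.

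This softens the conflict but does not remove it. The no-testing clause is separate from the clause on power, and in the protocol it stands under the general statistical heading. Comparative objectives can be met by estimation. Labelling the test exploratory would still mean dropping the verdict, which is the repair proposed here.

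Three smaller points stand:

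- No visible text ties the verdict to stopping or to a go/no-go decision. SAP Section 9.6.4 on study success is redacted, so whether it uses this test cannot be checked.
- The wrong product names are an editorial error; nobody would run the wrong comparison.
- The SDs and true differences are assumptions. At a true 2-point benefit, 'not achieved' is the less likely verdict for SDs of 1.5 to 2.5. The textual contradiction needs none of these numbers.

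**Conclusion.** The concern holds. The current SAP both requires and disclaims a formal superiority test of its primary efficacy endpoint, and the protocol sides with the disclaimer. This must be settled before results are known. The product names are a definite error in the sentence that sets alpha; the missing sign in the success rule is a lesser wording fault.

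Under the stated assumptions, the test would miss a true 1-point benefit more often than not at every SD considered. Only differences of about 1.6 to 3.2 points would be detected with 80% power. Dropout over 360 days would leave fewer observed values than assumed. The regression model, LS means and CI are not in question.

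**What to change.** In SAP Section 9.7.2.1.1:

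- Delete the sentence announcing the superiority evaluation, both hypotheses, the sentence on alpha with EXPAREL and bupivacaine HCl, and both decision rules.
- Replace "To test for significant differences between iovera^o and RFA group" with: *To estimate the difference between the iovera and RFA groups*.
- Keep the regression model, LS means and 95% CI.
- Add: *The LS mean difference (iovera − RFA) in NRS average pain at Day 360 and its two-sided 95% CI are an estimate for planning the full RCT. No hypothesis is formally tested. Any p-values for primary or secondary endpoints are exploratory.*

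The last sentence also covers the p-value that the section still reports and the secondary subsections that borrow the analysis.

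This is SAP wording only. The sponsor gives up a superiority claim that its protocol says it does not seek.

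If the sponsor prefers to keep a test, the section must name iovera and RFA and require the whole 95% CI for iovera − RFA on NRS to lie below 0. SAP Section 10 and the protocol's Statistical Methods must then be changed to allow it. That costs more, because it needs a protocol amendment as well as SAP changes.

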Appendix 4: Patients' Global Impression of Change (PGIC)

Subjects will complete the PGIC at Day 30 (\pm 5 days), Day 60 (\pm 5 days), Day 90 (\pm 5 days), Day 120 (\pm 5 days), Day 150 (\pm 5 days), Day 180 (\pm 5 days), Day 210 (\pm 7 days), Day 240 (\pm 7 days), Day 270 (\pm 7 days), Day 300 (\pm 7 days), Day 330 (\pm 7 days), Day 360 (\pm 7 days).

Patients' Global Impression of Change (PGIC) scale.

Name:	Date:	DOB:

Chief Complaint:

Since beginning treatment at this clinic, how would you describe the change (if any) in ACTIVITY LIMITATIONS, SYMPTOMS, EMOTIONS and OVERALL QUALITY OF LIFE, related to your painful condition? (tick ONE box).

No change (or condition has got worse)	0	1
Almost the same, hardly any change at all		2
A little better, but no noticeable change		3
Somewhat better, but the change has not made any real difference		4
Moderately better, and a slight but noticeable change		5
Better, and a definite improvement that has made a real and worthwhile difference	0	6
A great deal better, and a considerable improvement that has made all the difference		- 7

In a similar way, please circle the number below, that matches your degree of change since beginning care at this clinic:

Much Better				No Change					Much Worse	
0	1	2	3	4	5	6	7	8	9	10
Patient's sig	gnatur	e:					1	Date:		

Reference: Hurst H, Bolton J. Assessing the clinical significance of change scores recorded on subjective outcome measures. J Manipulative Physiol Ther 2004;27:26-35.

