9.7.2.2. Secondary Efficacy Analyses

9.7.2.2.1. NRS "average pain over past 24 hours" intensity scores from first pain assessment post-treatment (Day 1) to Day 30, Day 180, and Day 360

Analysis and presentation will be the same as that of the primary analysis for the primary efficacy endpoint as outlined in **Section 9.7.2.1.1**.

9.7.2.2.2. Changes in NRS pain intensity scores (“average pain over 24 hours) from pre-treatment until Day 360

The percent changes will be calculated for each subject as follows:

$$\% \text{ Change} = \{NRS_{\text{current}} - NRS_{\text{screening}}\} / NRS_{\text{screening}} \times 100\%.$$

The current pain will be used at each post-treatment visit, and the change of NRS current pain will be defined as post iovera^o/RFA - pre iovera^o/RFA. Analysis and presentation will be the same using percent changes as an outcome as that of the primary analysis for the primary efficacy endpoint as outlined in **Section 9.7.2.1.1**. However, the regression model will not incorporate adjustments for covariates.

9.7.2.2.3. Oswestry Disability Index scores from Day 30 to Day 360

Analysis and presentation will be the same as that of the primary analysis for the primary efficacy endpoint as outlined in **Section 9.7.2.1.1**.

9.7.2.2.4. Change in Oswestry Disability Index (ODI) scores from pre-treatment to Day 360

Analysis and presentation will be the same as that of the primary analysis for the primary efficacy endpoint as outlined in **Section 9.7.2.1.1**.

9.7.2.2.5. Patient’s Global Impression of Change (PGIC) from Day 30 to Day 360

Analysis and presentation will be the same as that of the primary analysis for the primary efficacy endpoint as outlined in **Section 9.7.2.1.1**.

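### The SAP's superiority rule tests only the p-value, so a significant Day 360 NRS result favouring RFA would, applied literally, be declared superiority of iovera

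*SAP*

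**What the plan says.** SAP 9.7.2.1.1 gives a directional alternative: "iovera^o is superior to RFA with respect to mean of NRS pain intensity scores at Day 360". The null is the complement, that iovera is not superior. The test is two-sided: "A two-sided hypothesis test will be performed at $\alpha=0.05$ level of significance". The contrast is iovera minus RFA, and two bullets turn the p-value into a verdict. In the first, the p-value "is >0.05 , then the superiority of iovera^o to RFA is not achieved". In the second: "If the p-value for the least squares mean treatment difference in NRS at Day 360" is at or below 0.05, "then the superiority of iovera^o to RFA is achieved". The section also plans LS means by arm and a two-sided 95% confidence interval for the difference, but neither bullet refers to them.

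Protocol Appendix 1 anchors the NRS at 0 for no pain and 10 for the worst possible pain.

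For PGIC, SAP 9.7.2.2.5 says: "Analysis and presentation will be the same as that of the primary analysis for the primary efficacy endpoint". It names neither an item nor a favourable direction. Protocol Appendix 4 contains two scored items. The first runs from 1, "No change (or condition has got worse"), to 7, "A great deal better, and a considerable improvement that has made all the difference". The second runs from 0 (much better) to 10 (much worse).

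**The concern.** A two-sided p-value carries no direction. The two bullets cover every possible p-value, so every significant result falls under the second one, whichever arm did better. On the NRS only a negative difference favours iovera. A significant positive difference means RFA patients had less pain, yet the bullet returns superiority of iovera. That outcome lies inside the SAP's own null hypothesis, so the rule can reject the null on evidence that supports it. What is at stake is the headline verdict on the primary efficacy endpoint.

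PGIC raises a smaller, related problem of direction. Until the SAP says which item is analysed, the sign of an iovera-minus-RFA difference cannot be interpreted.

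**Working it through.** **Inputs from the documents.** Alpha 0.05, two-sided, contrast iovera minus RFA, and model covariates baseline NRS, sex and tobacco status (SAP 9.7.2.1.1). 15 subjects per arm (SAP section 10). NRS lower is better (Protocol Appendix 1).

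**Assumptions.** The documents give no SD and no expected difference, so true effects are stated in SD units, d = (true RFA advantage)/SD. No dropout, normal errors.

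**1. The plan's own figure.** At d = 0 the two tails are 0.025 + 0.025 = 0.05, which reproduces the stated alpha. The rule counts both tails as iovera superiority, so it declares iovera superior in 5% of trials. A rule that also requires a negative difference keeps one tail, 2.5%.

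**2. When RFA is truly better.** The test statistic follows a noncentral t distribution with noncentrality d × √(n/2) = d × √(15/2) = 2.739d. The probability that the rule declares iovera superior is P(T > t_crit) + P(T < −t_crit). Only the second term would survive a sign condition.

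Simple two-sample t-test, df = 30 − 2 = 28, t_crit = 2.048:

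| d (RFA better) | Noncentrality | Rule as written | With sign condition |
|---|---|---|---|
| 0.5 | 1.369 | 0.262 | 0.0005 |
| 0.75 | 2.054 | 0.509 | 0.00004 |
| 1.0 | 2.739 | 0.753 | 0.000002 |

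With the three planned covariates, df = 30 − 2 − 3 = 25 and t_crit = 2.060. The probabilities are then 0.260, 0.506 and 0.749, so the choice of model hardly matters.

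**3. In NRS points (25 df).** With an assumed SD of 2.0, a true RFA advantage of 1, 2 or 3 points gives 0.26, 0.75 and 0.98. Over assumed SDs from 3.0 down to 1.5, the ranges are 0.14–0.42, 0.42–0.94 and 0.75–1.00. Because the null includes RFA being better, the rule's error rate over that null is not held at 0.05. It approaches 1 as the RFA advantage grows.

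**4. PGIC, by sign.** Take a negative iovera-minus-RFA difference. On the 1–7 item (higher better) it favours RFA. On the 0–10 item (lower better) it favours iovera. A sign condition copied from the NRS would therefore be wrong for the 1–7 item.

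**The case against.** The strongest reply is that direction is already in the section. The alternative is directional, the contrast is fixed, and the arm means and interval appear with the p-value. On this view the bullets are shorthand, and nobody looking at the table would call RFA's win a win for iovera. It stands that an attentive reader would notice the reversal. But these elements do not amend the bullets, which are the stated decision rule. The sentence introducing the bullets also names two products that are not this trial's arms, so the intended reading should not be left to inference.

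A second reply is that 26%, 51% and 75% are simply the power of a two-sided test under effects favouring RFA. That is correct. They become false verdicts only if the bullets are applied literally, and they should be quoted with that condition.

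A third reply is that SAP section 10 disclaims formal hypothesis testing, so the verdict should not exist. That is a separate matter. If the verdict goes, the sign defect goes with it.

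On PGIC, a reader might infer that the superiority rule itself is carried over to that endpoint. The documents do not support this. The cross-reference covers analysis and presentation, which most naturally means the regression, LS means, interval and p-value, while the hypotheses and bullets are worded only for NRS at Day 360. Nor does anything in the plan propose combining the two PGIC items. The lowest category of the 1–7 item merges no change with worsening, but that is a property of the instrument, not an error in the SAP.

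**Conclusion.** The concern holds for the primary rule. As written, SAP 9.7.2.1.1 returns superiority of iovera for any significant Day 360 NRS difference, including one favouring RFA, and so contradicts its own hypotheses. The size is about 26%, 51% and 75% at assumed RFA advantages of 0.5, 0.75 and 1.0 SD, and 5% instead of 2.5% at no difference. These figures rest on literal application of the bullets, 15 evaluable subjects per arm and effect sizes that the documents do not supply. They are not a forecast that the report will name the wrong arm, because the planned LS means and interval would expose it. SAP 9.6.4 on study success is redacted, so no consequence for overall study success can be inferred.

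For PGIC the conclusion is narrower: the item analysed and its favourable direction are not named.

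**What to change.** **If the verdict is kept:** in SAP 9.7.2.1.1, declare iovera superior only when the two-sided p-value is at most 0.05 and the difference (iovera minus RFA) is below 0. Apart from an exact tie at the boundary, this is the same as an upper 95% confidence limit below 0. State also that a lower limit above 0 favours RFA.

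**If the verdict is dropped to agree with SAP section 10:** the sign condition on it falls away. Report the difference with its interval and read it by direction.

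**In either case:** in SAP 9.7.2.2.5, name the PGIC item analysed, or report both items separately. State the favourable direction for each endpoint: lower for NRS; lower for ODI, assuming scoring in which higher means more disability, which the documents do not spell out; higher for PGIC 1–7; lower for PGIC 0–10; higher for the 1–5 satisfaction scale.

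The cost is a few sentences in the SAP, plus a second set of PGIC results if both items are reported. No new data are needed.
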